9.1 Sample Size, Accrual Rate and Study Duration

Though the plan is to enroll 15 participants to each of the 4 cohorts, we anticipate that there may be some dropout due to inability to continue therapy or undergo biopsy. We therefore inform our statistical calculations under the assumption that 12 participants in each group will yield results for analysis.

The number 15 chosen as a minimum number for evaluation for the following 3 reasons:

1) The prevalence of PD-L1 expression in SCLC is not well-characterized. In one basket study of pembrolizumab that enrolled ONLY patients who were PD-L1 positive, the rate of positivity among those screened was 28.6% (other factors may have had a selection bias in those who were screened for study), which would estimate that <4/12 patients would have positive PD-L1 expression from a diagnostic biopsy. We have NO information regarding the potential changes that may occur as a result of exposure to chemotherapy and radiation. Attempts at retrospective evaluation have been unsuccessful as below.

2) After screening > 220 SCLC patients for retrospective analyses of paired equivalent biopsies at DFCl, we were able to find exactly 3 pairs with adequate and comparable tissue which was one of the prompts to design this prospective trial. Most SCLC biopsies contain extensive crush artifact or often have scant tissue and the adequacy of prospectively collected tissue samples is also uncertain making it difficult to make statistical assumptions.

3) It is anticipated that it may be difficult to compare the pre and ON/POST treatment samples due to treatment effect as there is a high rate of response to therapy with both chemotherapy and radiation (therefore there may be extensive treatment effect or minimal tumor in biopsies done after exposure to

chemotherapy), but we won't know how difficult until the study is done because of the rarity of these on-treatment biopsies to know how tissue specimens will compare.

These considerations are the reason that the endpoint was built around the feasibility of getting comparable specimens for assessment of change in PD-L1 expression (i.e. being able to accurately measure from both to actually evaluate change).

Comparisons of paired biopsies will be conducted using the one-sample Wilcoxon signed rank test, which has 88% power to test that the mean of paired differences in 10% vs. 0% while testing at the 2-sided 0.05 level and assuming an effect size of 1.0. We plan to estimate event-time distributions of progression-free survival and overall survival using the Kaplan-Meier method, and any comparisons (for example, between groups defined by baseline PD-L1 expression level) will be made using the logrank test. Multivariable Cox models will be fitted to adjust for any known prognostic factors and landmark analyses may be conducted to explore any association between post-baseline PD-L1 expression levels and outcomes. Comparisons of baseline PD-L1 expression levels and response will be made either using Fisher's exact test (should a reasonable cutpoint defining 'positivity' in PD-L1 expression level be identified during this study) or Wilcoxon rank sum test.

We will analyze the data of circulating cytokines, and circulating T cell repertoire before, during, and after therapy with pembrolizumab and their relationship to clinical benefit with pembrolizumab therapy. Many of the statistical methods described above will apply, but we may also fit repeated measures models to data that is collected longitudinally. Identification of genetic changes using nextgen sequencing (oncopanel) and gene expression changes using nanostring before, during, and after therapy with pembrolizumab to determine relationship, if any, to clinical benefit with pembrolizumab.

10 Safety and Adverse Events

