3. TREATMENT PLAN

Each cohort will consist of 15 patients. All patients will be treated with up to 6 cycles of cis/carboplatin + etoposide. Eligible patients for consolidation thoracic radiotherapy will complete this within 6 weeks following completion of chemotherapy. All patients will be required to have pre-treatment biopsies prior to initiation of pembrolizumab for evaluation of PD-L1 expression and other correlative evaluations (within 4 weeks of start). Cohorts B-D will ALSO be required to submit a diagnostic biopsy specimen (prior to any treatment) for intra-subject comparison of PD-L1 expression between biopsies.

Cohort A will start pembrolizumab at the same time as starting standard chemotherapy with carboplatin + etoposide and receive all three drugs. Cohort B will start pembrolizumab after one cycle of cis/carboplatin/etoposide and receive all three drugs for the remaining cycles. Cohort C will consist of subjects who are not candidates for consolidation thoracic radiotherapy (thoracic RT) or prophylactic cranial irradiation (PCI) but who have completed 1st line therapy with 4-6 cycles of chemotherapy—these subjects will start pembrolizumab after completion of chemotherapy. Cohort D will consist of patients who have completed 4-6 cycles of carboplatin + etoposide as well as consolidation thoracic radiotherapy and/or PCI—these subjects will start pembrolizumab after completion of chemotherapy and radiation.

Pembrolizumab will be continued until progression following completion of standard treatment for all cohorts or for up to 2 years of therapy total.

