6. CORRELATIVE STUDIES

Diagnostic biopsy specimens (20 slides) from all participants will be evaluated for PD-L1 expression on tumor cells as well as within the tumor microenvironment. For cohorts B-D, an additional mandatory biopsy specimen will also be evaluated and compared to the diagnostic biopsy specimen. Optional post-treatment biopsies will also be collected. All tumor specimens will be evaluated for PD-L1, CD3, FOXP3, TIM3, LAG3 and other immune biomarkers if sufficient tissue available. Next-gen sequencing-based genotyping and gene expression profiling using nanostring will be performed from pre-treatment biopsies from all participants. A subset who have fresh tissue samples collected will also have immune profiling and whole-exome sequencing performed. All participants will have blood samples collected pre, during, and post-treatment for evaluation of soluble PD-L1 and cytokine profiling as well as possible sequencing.

SCHEMA

Pembrolizumab therapy starts at different time points for each cohort

- A) concurrent with cycle 1 chemotherapy
- B) after cycle 1 (concurrent therapy)
- C) after completion of 4-6 cycles of chemotherapy (maintenance monotherapy)
- D) after thoracic radiation+/- prophylactic cranial irradiation (maintenance monotherapy)

Biopsies:

- a) Cohort A will have single required diagnostic biopsy
- b) Cohort B will have diagnostic biopsy and required pre-treatment with pembrolizumab biopsy (after cycle 1 chemotherapy)
- c) Cohort C will have diagnostic biopsy and required pre-treatment with pembrolizumab biopsy (after completion of 4-6 cycles chemotherapy)
- d) Cohort D will have diagnostic biopsy and required pre-treatment with pembrolizumab biopsy (after completion of chemotherapy and radiation).

Core biopsy prior to pembrolizumab required for all cohorts in addition to diagnostic biopsy for cohorts B-D (Diagnostic biopsy must be core or greater to allow for paired biopsy comparisons).

1 Introduction

This document is a protocol for a human research study. This study is to be conducted in accordance with US government research regulations, and applicable international standards of Good Clinical Practice, and institutional research policies and procedures.

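### The 88% power in section 9.1 matches a paired t-test; with 12 pairs and normal differences, the signed-rank test held at two-sided 0.05 has about 85%

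*Combined protocol and SAP*

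**What the plan says.** Section 9.1 of the combined protocol and SAP contains the only power statement for the primary objective, the change in PD-L1 expression.

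- **Test:** "Comparisons of paired biopsies will be conducted using the one-sample Wilcoxon signed rank test".
- **Level:** "testing at the 2-sided 0.05 level".
- **Alternative and power:** the "one-sample Wilcoxon signed rank test, which has 88% power to test that the mean of paired differences in 10% vs. 0" (percent), with an assumed effect size of 1.0.
- **Sample size:** the power sentence does not repeat it. Earlier in the same section, 15 are to be enrolled per cohort and the calculations assume that "12 participants in each group will yield results for analysis".

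The section does not say whether the signed-rank test is exact or based on a large-sample approximation. It gives no distribution for the differences and no method for the power calculation.

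The pairs themselves are defined elsewhere. The Treatment Plan in the front matter says "Cohorts B-D will ALSO be required to submit a diagnostic biopsy specimen (prior to any treatment) for intra-subject comparison of PD-L1 expression" between biopsies, and the schema says "Cohort A will have single required diagnostic biopsy".

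**The concern.** The sentence fixes the test, the level and the effect size, and the section supplies the number of pairs. Once a distribution is assumed, these inputs determine the power. Under the usual assumption of normal differences, they do not give 88% for a signed-rank test that respects the 0.05 level. They do give it for a different test, the paired t-test.

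Little is at stake beyond accuracy. No decision rule uses the 88%. A reader should still be able to reproduce the headline power of the primary analysis from the test that the plan names.

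**Working it through.** **Inputs.** From section 9.1: n = 12 pairs, standardised effect d = 1.0, two-sided α = 0.05. The mean difference of 10 points and d = 1.0 imply an SD of 10 points. Normal differences are an assumption made here; the documents name no distribution.

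**Step 1: reproduce the stated figure (paired t-test).** Degrees of freedom are 12 − 1 = 11, and the noncentrality is d√n = √12 = 3.464. The two-sided critical value is 2.201. Power from the noncentral t distribution is 0.8829, or 88.3%. This matches 88%.

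**Step 2: rejection region of the exact signed-rank test.** Let W be the smaller rank sum. With 12 pairs there are 2¹² = 4096 equally likely sign patterns under the null.

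- Reject at W ≤ 13: 2 × 87/4096 = 174/4096 = 0.0425.
- Reject at W ≤ 14: 2 × 107/4096 = 214/4096 = 0.0522.

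A test held at 0.05 must therefore stop at W ≤ 13.

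**Step 3: large-sample versions.** Under the null, W has mean 12 × 13/4 = 39 and variance 12 × 13 × 25/24 = 162.5, so the SD is 12.75.

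- Uncorrected, W = 14: z = 25/12.75 = 1.961, p = 0.0499. It rejects, so its region is W ≤ 14 and its true size is 0.0522.
- Continuity-corrected, W = 14: z = 24.5/12.75 = 1.922, p = 0.0546. It does not reject, so its region is the same as that of the exact test.

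**Step 4: power with normal differences** (simulation, 1,000,000 runs or more, Monte Carlo error about 0.04 points or less).

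| Test, 12 pairs, d = 1.0 | True size | Power |
|---|---|---|
| Paired t-test | 0.050 | 88.3% |
| Signed-rank, uncorrected approximation (W ≤ 14) | 0.0522 | 87.5% |
| Signed-rank, exact or continuity-corrected (W ≤ 13) | 0.0425 | 85.0% |

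The gap to the stated figure is 88 − 85.0 = 3.0 points.

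**Step 5: sensitivity to shape** (exact test, 12 pairs, d = 1.0, no zero differences).

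| Shape of differences | Power |
|---|---|
| Uniform | 80.5% |
| Gamma, left skew (0.5 to 1.0) | 82% to 81% |
| Normal | 85.0% |
| Logistic | 86.2% |
| Laplace | 87.1% |
| t, 5 df | 87.9% |
| Gamma, right skew 0.5 | 88.7% |
| t, 4 df | 89.3% |
| Gamma, right skew 0.71 | 90.5% |
| Gamma, right skew 1.0 | 93.5% |

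**Step 6: sensitivity to the number of pairs** (exact test, normal differences). Power is 81.0% with 11 pairs, 85.0% with 12, 89.5% with 13 and 93.8% with 15.

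**The case against.** The strongest reply is that section 9.1 says neither exact nor normal, so 85% rests on two assumptions that the reviewer supplies. The stated figure can be reproduced: 88.3% from the t-test, and 87.5% from the uncorrected signed-rank approximation. Step 5 also shows the exact test reaching about 88% or more with heavier tails or mild right skew. Right skew is plausible here. Section 9.1 expects fewer than 4 of 12 diagnostic biopsies to be PD-L1 positive, and a pair that starts at zero cannot fall.

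Most of this stands. A reader might infer that 88% is an arithmetic error without any basis, or that 85% is the true power. The documents support neither. Both figures are conditional, and the plan does not state the condition behind its own. What remains is that 88% is not the power of the named test at the named level under normal differences. Its closest match is the t-test, and that origin is an inference because the plan does not give its method.

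A reader might also infer that section 9.1 claims paired power for all four cohorts, since it speaks of 12 in each group. The text does not support that. The power sentence opens with paired biopsies, and section 4.1 (criterion 11) and section 6.6.7.1 require the second specimen only in cohorts B to D. Naming those cohorts is a clarification and does not correct a contradiction.

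**Conclusion.** The point holds in a limited form and is minor. With 12 pairs, normal differences and effect size 1.0, a signed-rank test kept at or below two-sided 0.05 has about 85% power, 3 points below the stated 88%. The stated figure is mislabelled and depends on assumptions that the plan does not give.

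It would be wrong to conclude that the trial is underpowered. Power stays above 80% with normal differences and with every other continuous shape tried, and neither the sample size nor any decision depends on the 3 points. Neither 85% nor 88% allows for pairs that show no change at all. The documents do not give the share of such pairs, so no figure can be fixed for it.

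**What to change.** Replace the power sentence in section 9.1 with one that states its conditions, for example:

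> With 12 pairs per cohort (cohorts B, C and D), a mean paired difference of 10% vs. 0%, effect size 1.0 and normally distributed differences, the exact signed rank test has about 85% power at the 2-sided 0.05 level.

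If the sponsor had another distribution or test version in mind, naming it beside the matching figure would serve equally well.

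Three additions are optional and not part of the correction: a note that the exact test cannot reach 0.05 with fewer than 6 non-zero pairs (5 of 5 in one direction gives 2/32 = 0.0625), exact confidence intervals for each cohort's change, and a supplementary stratified test pooling the pairs from cohorts B to D.

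The cost is one reworded sentence and a headline power about 3 points lower. Sample size, enrolment and procedures do not change.

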3.3 Secondary Study Endpoints

- To evaluate progression-free survival with the addition of pembrolizumab to standard therapy
 - endpoint: to evaluate median progression-free survival in overall population with stratification by cohort as compared to historical control of 5.4 months³¹
- To evaluate overall survival with the addition of pembrolizumab to standard therapy
 - Endpoint: to evaluate median overall survival in overall population with stratification by cohort as compared to historical control of 9.5 months.³¹
- To evaluate response rates by RECIST 1.1 and irRC (as adapted to RECIST 1.1³²) with the addition of pembrolizumab to standard therapy (for cohort A only)
 - Endpoint: response rate at 6 and 12 weeks after initiation of pembrolizumab therapy as measured by RECIST 1.1 and irRC (as adapted to RECIST 1.1³²)

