8.1.6 Survival outcomes

Overall Survival: Overall Survival (OS) is defined as the time from randomization (or registration) to death due to any cause, or censored at date last known alive.

Progression-Free Survival: Progression-Free Survival (PFS) is defined as the time from randomization (or registration) to the earlier of progression or death due to any cause. Participants alive without disease progression are censored at date of last disease evaluation.

Time to Progression: Time to Progression (TTP) is defined as the time from randomization (or registration) to progression, or censored at date of last disease evaluation for those without progression reported.

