SCLC provides an opportune setting to evaluate the potential importance of variability in PD-L1 expression and its influence on optimizing timing of checkpoint inhibition. All extensive-stage SCLC patients are treated with chemotherapy and recent data suggests added benefit to consolidation thoracic radiation¹⁰.

The proposed study seeks to evaluate pembrolizumab therapy initiated at different times during the course of SCLC treatment: a) up front, in conjunction with initiation of chemotherapy, b) starting after one cycle of chemotherapy, c) starting after completion of 1st line chemotherapy, d) starting after completion of consolidation thoracic radiation therapy and/or PCI. Treatment with pembrolizumab will be preceded by biopsy for evaluation of PD-L1 expression with correlative evaluation of changes in PD-L1 expression (relative to diagnostic biopsy) and changes in other tissue- and blood-based biomarkers and immune markers. The study is based on the following hypotheses:

- 1) PD-L1 expression is dynamic and can increase with exposure to chemotherapy and/or radiation
- 2) PD-L1 expression influences efficacy of pembrolizumab=
- 3) Pembrolizumab can improve outcomes in SCLC

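### Section 9.1 does not name cohort as a stratum in the analyses relating PD-L1 to PFS and OS, so a PD-L1 measure taken after chemotherapy or radiation can pick up cohort differences

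*Combined protocol and SAP*

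**What the plan says.** Section 9.1 relates PD-L1 to outcome in four ways.

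- PFS and OS by PD-L1 group: "any comparisons (for example, between groups defined by baseline PD-L1 expression level) will be made using the logrank test".
- Adjustment: "Multivariable Cox models will be fitted to adjust for any known prognostic factors". Cohort is not named among the factors.
- Later PD-L1 measurements: "landmark analyses may be conducted to explore any association between post-baseline PD-L1 expression levels and outcomes".
- Response: "Comparisons of baseline PD-L1 expression levels and response will be made either using Fisher's exact test", or a Wilcoxon rank sum test if no cutpoint is found.

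Cohort appears in section 3.3, where the PFS endpoint is "to evaluate median progression-free survival in overall population with stratification by cohort as compared to historical control of 5.4 months"; OS is worded the same way against 9.5 months. That stratification belongs to the medians. Section 3.3 also gives the response endpoint as "with the addition of pembrolizumab to standard therapy (for cohort A only", a limit that section 2.2 does not carry.

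Two other places set up the problem. The first hypothesis listed at the start of section 9 is that "PD-L1 expression is dynamic and can increase with exposure to chemotherapy and/or radiation". Section 8.1.6 fixes the clock: "Progression-Free Survival (PFS) is defined as the time from randomization (or registration) to the earlier of progression or death due to any cause". OS has the same origin.

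**The concern.** The cohorts are not exchangeable on PFS or OS. Registration falls before any treatment in A, after one cycle in B, after 4-6 cycles in C, and after chemotherapy and radiation in D. Section 4.1 excludes prior progression in B, C and D, and section 4.2 excludes complete responders to earlier therapy. Under Table 2 of section 5.2, A and B receive pembrolizumab with chemotherapy, while C and D receive it alone. Time from registration to progression or death can therefore differ by cohort whatever PD-L1 does.

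If PD-L1 is measured after chemotherapy or radiation and rises with it, as hypothesis 1 allows, PD-L1-positive participants will be over-represented in C and D. Prior treatment then drives both the marker and the outcome. An analysis that ignores cohort could suggest support for hypothesis 2 (that PD-L1 influences the efficacy of pembrolizumab) when there is no effect, or hide an effect that exists.

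**Working it through.** **The plan's own figure.** Section 9.1 gives one power figure, 88% for the paired-biopsy test. A noncentral t calculation with n = 12, effect size 1.0 and two-sided 0.05 gives 88.3%, so it reproduces and confirms 12 per cohort as the planning number. The plan gives no operating characteristics for the PD-L1-outcome tests.

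**Which biopsy is baseline?** The plan points both ways.

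- Diagnostic biopsy: section 9.1 sets baseline against post-baseline PD-L1, and section 3.1 uses the word for cohort A's untreated biopsy. Every cohort supplies a pre-treatment diagnostic specimen.
- Pre-pembrolizumab biopsy: elsewhere baseline means shortly before protocol therapy (21 days in section 7, 28 days for scans in section 6.6.5, 4 weeks in section 8.1.3). In C and D the diagnostic biopsy precedes 4-6 three-week cycles, that is at least 12-18 weeks of chemotherapy. The new biopsy required by section 4.1 item 11, within 4 weeks of treatment, fits those windows.

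**Inputs.** From the documents: 12 analysable per cohort (section 9.1), 28.6% positivity at diagnosis (section 9.1), and 5.4 months as historical median PFS (section 3.3). Assumed: medians of 2.5 or 4 months in C/D, positivity other than 28.6%, exponential times, and censoring at 24 months. Section 9.1 says that nothing is known about change in PD-L1 after treatment.

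**How the mix shifts.** At 29% in A/B and 60% in C/D:

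- positives: 24 × 0.29 = 6.96 from A/B and 24 × 0.60 = 14.4 from C/D, so 14.4/21.36 = 67% come from C/D;
- negatives: 17.04 from A/B and 9.6 from C/D, so 9.6/26.64 = 36% come from C/D.

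The hazard is ln 2/median: 0.128 per month at 5.4 months and 0.277 at 2.5 months, a ratio of 2.16. With equal positivity, both groups draw half their members from C/D and the mix does not shift.

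**Tests compared.** The unstratified log-rank statistic is (O − E)²/V over all participants. The stratified one is (Σ(Oₛ − Eₛ))²/ΣVₛ over cohorts s. Each is referred to 3.841. Results are simulated, 12 per cohort; repeated runs agree to within about a point.

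| Positivity A/B vs C/D | Median PFS A/B vs C/D (months) | True PD-L1 HR | Unstratified rejects | Stratified rejects |
|---|---|---|---|---|
| 28.6% in all | 5.4 vs 2.5 | 1.0 | about 6% | about 6% |
| 29% vs 50% | 5.4 vs 2.5 | 1.0 | about 9% | 5-6% |
| 29% vs 60% | 5.4 vs 2.5 | 1.0 | about 13% | about 5% |
| 29% vs 60% | 5.4 vs 4 | 1.0 | 6-7% | about 5% |
| 20% vs 70% | 5.4 vs 2.5 | 1.0 | about 25% | 5-6% |
| 29% vs 60% | 5.4 vs 2.5 | 0.5 | 26% (power) | 48% (power) |
| 28.6% in all | 5.4 vs 5.4 | 0.5 | about 48% (power) | about 42% (power) |

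A second set of assumptions, with graded positivity and C/D medians of 2 or 3 months, gave 6.9-14.7% unstratified and 5.1-6.1% stratified. When positivity differed but prognosis did not, the unstratified rate was 6.1%. Both links are needed for inflation.

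**Response.** If response were pooled over four cohorts, with positivity 28.6/40/60/60% and assumed response rates of 60/60/15/15% or 70/50/10/10%, Fisher's test would reject falsely in 10.8-13.8% of trials. With 28.6% in every cohort it rejects in about 3%. Within cohort A alone there is no between-cohort confounding.

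**Limit.** The landmark analysis may use B-D only, since A has no second required biopsy. The table covers all four cohorts, taking A's single biopsy as its pre-pembrolizumab value.

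**The case against.** The strongest objection is that the quoted log-rank test, and the response test, use baseline PD-L1. If that is untreated diagnostic tissue, hypothesis 1 creates no link with cohort, and the unstratified rate stays at about 6%. This stands. It does not dispose of the point, because the term is undefined. If baseline means diagnostic, the pre-pembrolizumab biopsy becomes a post-baseline value and enters the landmark analysis, which also names no cohort stratum. The circulating markers raise the same issue: section 9.1 extends many of these methods to them, and section 6.6.7.2 starts blood sampling at screening, which is after chemotherapy in C and D.

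It is also fair to say that the Cox models could include cohort, and that section 3.3 shows the authors had cohort stratification in mind. Neither commits the PD-L1 analyses to it.

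A reader might infer more: that PD-L1 is a proxy for cohort, that every PD-L1 test is compromised, and that false positives reach 28%. The documents do not support this. Hypothesis 1 says only that expression can increase. Section 3.3 limits response to cohort A, so a pooled response test is not established. A figure near 28% needs 15 rather than 12 per cohort and positivity of 20% against 70%, which no section gives. Finally, section 6.7.1 calls these biomarker-benefit studies exploratory, and no decision rule attaches to hypothesis 2.

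**Conclusion.** The point holds as an inexpensive improvement to an exploratory analysis. Section 9.1 names no cohort stratum for any analysis of PD-L1 against PFS or OS, and the cohorts differ in ways that affect both outcomes. With diagnostic PD-L1 the log-rank test is not materially affected. With PD-L1 from the pre-pembrolizumab biopsy, false rejection is about 9-13% under the central assumptions, ranging from 6-7% if C/D medians are 4 months to about 25% at 20% vs 70% positivity; stratification holds it at about 5-6%. Power for a true hazard ratio of 0.5 can fall to 26% where a stratified test would have 48%. All of this rests on assumed cohort medians and post-treatment positivity. The primary paired-biopsy comparison is unaffected.

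**What to change.** In section 9.1:

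1. State which biopsy defines baseline PD-L1 in each cohort, and which specimens count as post-baseline.
2. Stratify by cohort every log-rank, Cox and landmark analysis that relates PD-L1 or another biomarker to PFS or OS.
3. Reconcile sections 2.2 and 3.3 on whether response is analysed beyond cohort A. Only if it is, replace the pooled Fisher or rank sum test with a cohort-stratified exact (Mantel-Haenszel) or van Elteren test.

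This changes wording only and needs no new data. It is not free statistically. If the cohorts in fact share the same prognosis, stratification lowers power from about 48% to about 42% at 12 per cohort, hazard ratio 0.5 and 28.6% positivity throughout. If positivity is also 29% vs 60%, the fall is from about 58% to 47-49%.
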